4.1 Primary endpoint

Diagnosed pathology-verified breast cancer; to be followed up at three time-points: (i) screen-detected - diagnosed after being recalled at the screening examination, (ii) adding non-screen-detected cancer diagnosed within 12 months after the screening examination and (iii) adding non-screen-detected cancer diagnosed within 23 months after the screening examination, not including the following screening examination (such that all cancers diagnosed over a full screening cycle are captured).

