4.3.2 Cancer characteristics

- invasiveness by categories: in-situ only, invasive
- histology by categories: ductal, lobular, other
- tumor grade by categories: 1, 2, 3
- lymph node metastasis by categories: 0 nodes, 1-3 nodes, 4+ nodes
- tumor size, median size of invasive component and in situ component
- invasive tumor size by binary categories: (i) 0-19 mm, (ii) 20 mm+;
and by five categories: 0-9 mm, 10-19 mm, 20-29 mm, 30-49 mm, 50 mm+
- receptor status ER, PR, HER2 by categories: positive, negative
- proxy molecular subtype defined by:
 - Luminal A: ER+/PR+/HER2-; ER+/PR-/HER2-; ER-/PR+/HER2
 - Luminal B : ER+/PR+/HER2+; ER+/PR-/HER2+; ER-/PR+/HER2+
 - Non-luminal HER2-overexpressing: ER-/PR-/HER2+
 - Triple negative: ER-/PR-/HER2-

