Subgroup analyses will be performed for patient and cancer characteristics listed in 4.3 Additional data collected in the study. Statistical tests for effect heterogeneity across subpopulations will be performed by jointly testing the interaction (product) terms in generalised linear models or marginal models(10), as appropriate. No correction for multiple comparisons will be made.

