5.1 Populations

The study population consists of all consecutive women attending regular screening mammography at Capio S:t Göran hospital in Stockholm (excluding, by necessity, any time period when the AI system is not functional). The data for each woman consists of: mammographic images, date of examination, age at examination, breast density measure, assessment by first radiologist, assessment by second radiologist, assessment by AI, assessment by consensus discussion (if any), pathology-verified cancer diagnosis (if any) including key cancer characteristics (listed above under 4.1 and 4.2).

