5.5.4 Describe and compare the distribution of patient and cancer characteristics (described in 4.2.4) and stage (according to AJCC 7 and 8) between the two reader combinations in the primary analysis.

OTHER SECONDARY ANALYSES

5.5.5 Determine initial read operating characteristics (Table 1) for each combination of (i) initial read and (ii) arbitration as described in Figure 2.

5.5.6 Determine initial read operating characteristics for AI-only read below, and AI plus first-reader radiologist above, various AI score cut-off points.

5.5.7 Determine arbitration operating characteristics for an initial read by AI and one radiologist followed by either (i) the actual consensus discussion or (ii) arbitration decision based on recall of concordant cases and arbitration by second radiologist-decision for discordant cases.

5.5.8 Compare whether the cancer characteristics are different for the initial read cases flagged and not flagged between the AI reader and the radiologist readers.

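### At 12 and 23 months, analysis 5.5.8 compares tumour size and nodes recorded at diagnosis, so part of any flagged-versus-unflagged difference reflects later measurement

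*Combined protocol and SAP*

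**What the plan says.** Three parts of the SAP use cancer characteristics as analysis variables.

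- 5.5.8: "Compare whether the cancer characteristics are different for the initial read cases flagged and not flagged between the AI reader and the radiologist readers". No time-point is given.
- 5.5.4 compares characteristics and "stage (according to AJCC 7 and 8) between the two reader combinations in the primary analysis".
- The heterogeneity paragraph in section 5: "Subgroup analyses will be performed for patient and cancer characteristics listed in 4.3 Additional data collected in the study".

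The list in 4.3.2 includes "tumor size, median size of invasive component and in situ component", a 20 mm cut ("invasive tumor size by binary categories: (i) 0-19 mm, (ii) 20 mm") and "lymph node metastasis by categories: 0 nodes, 1-3 nodes, 4+ nodes". Stage is not on that list; only 5.5.4 names it.

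The cancer set is layered. Endpoint 4.1 starts with screen-detected cancers, adds later diagnoses to 12 months, and ends by "adding non-screen-detected cancer diagnosed within 23 months after the screening examination, not including the following screening examination". Section 5 says that analyses with clinical cases follow on the second and third database releases.

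In 5.1 each woman's data include a "pathology-verified cancer diagnosis (if any) including key cancer characteristics", and the protocol (Data collection methods) takes the characteristics from the hospital's medical records. No size measurement on the index mammogram is planned. That size and nodes are recorded at diagnosis is therefore an inference, but a strong one.

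**The concern.** A cancer that nobody flags is not recalled. It is found later, and its size and nodes are recorded then. For these variables the flagging decision partly determines the recorded value, whereas the planned comparison treats the value as a feature that the reader faced on the index image. The second exploratory objective in 4.4 takes that same direction, asking how characteristics influence performance.

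A follow-up paper could then report that a reader tends to miss large or node-positive cancers when part of the difference is delay. Some late diagnoses will also be cancers that arose or grew fast after the screen, and a pooled comparison cannot separate these from delay. Section 5.5 and Table 1 do warn about new cancers during follow-up, but only for counts of true and false negatives.

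**Working it through.** **1. Where the lag can enter.** Use the SAP's cells for cancers: a (both combinations positive), b and c (one positive), d (neither). AI plus first reader and first plus second reader together cover all three readers, so cell d is the set of cancers that no reader flagged.

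- 5.5.8 sets each reader's flagged cancers against those it did not flag. Cell d falls in every reader's unflagged group and is measured late.
- rTPF = (a+b)/(a+c) does not contain d, and 5.5.4 compares the cancers of the two combinations, so d is in neither. Lag enters only through cancers flagged but dismissed at consensus. (AI-flagged examinations that, as 5.9 describes, never reach consensus would act in the same way.)
- A cancer missed by one reader, flagged by another and diagnosed after recall is measured at screening and has no lag.
- With screen-detected cancers only, the problem does not arise.

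**2. The plan's power figure and reader overlap.** Inputs from 5.7: 55,000 women, prevalence 0.5%, TPF 0.70, rTPF 1.02, margin 0.85, one-sided alpha 0.025. Cancers: 55,000 × 0.005 = 275. TPF of AI plus radiologist: 0.70 × 1.02 = 0.714. The fraction positive on both combinations (TPPF) is not stated; it can lie between 0.414 and 0.70.

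Power = Φ(log(1.02/0.85)/SE − 1.96), with SE = √((b+c)/((a+b)(a+c))).

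At TPPF 0.467: b+c = 275 × (1.414 − 0.934) = 132, a+b = 196.35, a+c = 192.5, SE = 0.0591, and power = Φ(0.182/0.0591 − 1.96) = 87%. TPPF of about 0.45-0.48 gives 85-89%. The minimum, 0.414, gives 79.7%.

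**3. Cancers that no reader flagged.** d = 275 × (1 − 0.70 − 0.714 + TPPF) = 275 × (TPPF − 0.414).

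| TPPF | d |
|---|---|
| 0.45 | 10 |
| 0.48 | 18 |
| 0.70 (complete overlap) | 79 |

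The number flagged but dismissed comes on top and is unknown.

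**4. Possible distortion in 5.5.8.** No figure here is in the documents. Assumed: no true size difference at the index screen; median 12 or 15 mm with log-SD 0.5; volume doubling time (DT) 150-300 days; diagnosis uniform over follow-up (365 or 700 days); late-diagnosed share 50% of unflagged against 5% of flagged cancers, or 80% against 10%. Diameter grows by 2^(t/(3·DT)).

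Spurious difference = (late share, unflagged − late share, flagged) × (P1 − P0), where P0 and P1 are the proportions of 20 mm or more at the index screen and at late diagnosis.

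Example (15 mm, 200 days, 50% against 5%): P0 = 28%. At 12 months 36% of unflagged and 29% of flagged cancers reach 20 mm; at 23 months 43% and 30%. Over the whole grid the difference is about 4-15 points at 12 months and 8-27 at 23 months.

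**5. Smaller late shares.** On the plan's figures AI alone cannot detect more than 0.714, so it leaves at least 275 × 0.286 = 79 cancers unflagged. With d of 10-18, cell d is at most 10/79 = 13% to 18/79 = 23% of them. P1 − P0 over the grid is 0.08-0.21 at 12 months and 0.17-0.38 at 23 months. Against 5% of flagged cancers, the factor is 0.08-0.18, giving about 1-4 points at 12 months and 1-7 at 23 months. Cancers flagged by another reader but dismissed would raise the late share.

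**The case against.** The case against a broader criticism is strong, and much of it stands.

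- *Scope.* A reader might infer that 5.5.4 and the interaction tests suffer the same reverse causation as 5.5.8. They do not: cell d drops out. 5.5.4 also stands among the sensitivity analyses of the primary analysis, and Figure 3 labels the primary endpoint screen-detected cancer.
- *Direction.* In 5.5.8 a dismissed cancer belongs to the flagged group of whoever flagged it, which partly offsets the bias.
- *Number.* A reader might take 30% of 275, about 82, as measured late. That counts cancers missed by two radiologists; here AI flags also go to consensus. A figure near 82 needs almost complete overlap.
- *Reversal.* A reader might infer that sensitivity by size could change sign. Take 100 small cancers with sensitivity 65% and 100 large with 85%. If half of the 35 missed small cancers pass 20 mm, the result is 65/82.5 = 79% against 85/117.5 = 72%. This treats every miss as diagnosed late. If half of the 35 are caught by another reader and half of the rest pass 20 mm (8.75), it is 65/91.25 = 71% against 85/108.75 = 78%, with no reversal. The SAP names no analysis of sensitivity by size or nodes.
- *Time-point.* 5.5.8 does not say that it pools; endpoint (i) is screen-detected only and is the focus of the first manuscript.

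One argument stands only in part: that cancers missed by all readers are shared by AI and radiologists, so their lag cancels between readers. If the background sensitivities (81.9% AI, 77.4% first reader) carried over, there would be 18.1 and 22.6 misses per 100. The same shared cancers would then form a share 22.6/18.1 = 1.25 times as large among the AI's misses.

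These points narrow the concern without removing it. The later databases are planned, and no rule for these comparisons separates detection modes. The image studies in 5.6.6 and 5.6.8 do not correct size, nodes or stage.

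**Conclusion.** The concern holds for 5.5.8 when it is run on the 12- and 23-month cancer sets. Size and nodal differences between flagged and unflagged cancers would mix what the reader missed with later measurement and with new or fast-growing disease. For 5.5.4, including AJCC stage, and for the rTPF-based subgroup tests, lag enters only through cancers flagged but dismissed at consensus. The screen-detected analysis and its non-inferiority conclusion are not affected.

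The size is not determined by the documents. It depends on growth, on reader overlap and on how many flagged cancers consensus dismisses. The ranges in the working are illustrations, and the larger ones need late shares well above what cell d supplies at the overlap that reproduces 87% power. It also rests on the inference that size and nodes are recorded at diagnosis. The documents do not support the stronger conclusion that missed cancers would look advanced solely because they were missed, nor that the bias must favour AI.

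**What to change.** In 5.5.8, 5.5.4 and the heterogeneity paragraph:

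1. State the time-point, and so the cancer set, for each comparison.
2. At 12 and 23 months, report and compare size, nodes and stage separately for screen-detected and later-diagnosed cancers. Name the screen-detected comparison as the one measured at a common time.
3. Limit pooled comparisons to features treated as fixed, such as histology and receptor status.
4. Correct the cross-reference in 5.5.4: it cites 4.2.4 (process failures), while the characteristics are in 4.3.

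This costs SAP wording and one stratification, with no new data. There are two downsides. Each comparison has fewer cancers. The screen-detected stratum is also conditional on recall by a consensus that saw the AI output, and it leaves out the cancers that every reader missed. For that reason it should not be the only analysis, and the conditioning should be stated when it is interpreted.

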5.6 Exploratory analyses

5.6.1 Determine the initial read operating characteristics of a binary detection at each possible cut-off point for the AI scores based on the ground truth of cancer defined by end-point 4.2.1 and 4.2.2.

5.6.2 Determine the sensitivity of radiologist and AI depending on mammographic density (divided into four categories) and patient age (divided by 10-year intervals).

5.6.3 Determine whether the joint decision by AI and radiologist is more often false positive or false negative depending on the overall sensitivity and specificity of the radiologist with whom the AI decision is combined.

5.6.4 a) Sample the time and number of cases for a sample of consensus discussions during one or more weeks before use of the AI system, and at various time-points after taking the AI system

into use. Compare if there is a difference in the total time of consensus discussion for a standardized number of screening examinations, and if there is a difference in the time per case in the consensus discussions. b) Distribute a query based mainly on the Technology Acceptance Model 3 to all staff, and especially important to the radiologists participating in the consensus discussion. Have radiologists complete a mini-survey at the end of each consensus discussion.

5.6.5. a) Determine the operating characteristics of AI and radiologist for the following excluded groups: prior breast cancer and breast implants. b) To the extent possible, determine the sensitivity of flagging by radiologist and by AI for diagnosed women stratified by each characteristic listed in 4.3.1.2.

5.6.6 Determine differences in visual radiological characteristics between cases (i) not flagged by AI and (ii) not flagged by a radiologist to determine systematic differences between the two groups.

5.6.7 Examine a random selection of healthy women flagged by AI but not by any of the two initial read radiologists, and not recalled, to understand to what extent prior images or clinical information could have contributed to or averted a false positive read.

5.6.8 Examine all cases where at least one reader (AI or any radiologist) made a true positive initial read and at least one reader (AI or any radiologist) made a false negative initial read. Perform a reader study to identify potential image-related findings explaining the false negative assessments.

5.6.9 Examine the tendency of the consensus discussion to make more false-negative or more false-positive assessments (in terms of end-point 4.2.2 including interval cancers) depending on whether the initial read assessments were concordant, discordant with AI flagging and no radiologist, discordant with one radiologist flagging, other discordant flagging.

5.6.10 Determine the sensitivity difference between the combinations of AI and radiologists stratified by women 40-41 years old (initial screen) and women in subsequent screens.

5.7 Sample size

The sample size calculation relates to the primary analysis after women have undergone the baseline mammogram. Power for the additional two follow-up time points (at 12 and 23 months) will be higher, since there will be a larger number of cancers detected in the study at these time points than at the first time points (3 months).

The sample size calculation follows the methods for paired screen positive designs described in Alonzo, Pepe, and Moskowitz (9). The sample size calculation is based on the following assumptions: A prevalence of breast cancer in the screening of 0.5%, 0.70 TPF for a mammogram, and rTPF (AI+radiologist vs. SOC) equal to **1.02**. The non-inferiority margin was set to 0.85 and a one-sided alpha to 0.025. For the sample size calculations, we assumed that every woman who is recommended to undergo a biopsy also does so. Based on these assumption, 55,000 women will be included in the study giving a power of 87%.

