Analyses will compare the true positive fraction between different combinations of readers (radiologists or AI). Comparisons will be made on a relative scale. The relative true positive fraction (rTPF) is defined as TPF_r/TPF_{SOC} , where TPF_r is a specific reader combination r (Figure 2) being compared with the TPF of using two radiologists (SOC). The analysis will largely follow the methods described by Pepe and Alonzo (10).

The rTPF is estimated as $(a+b)/(a+c)$ (or $(a+c)/(a+b)$, as appropriate) and an approximate $100(1-\alpha)\%$ two-sided confidence interval for rTPF is calculated as

$$\exp\left(\log(\widehat{rTPF}) \pm z_{\alpha/2} \sqrt{\frac{b+c}{(a+b)(a+c)}}\right).$$

Analogous formulas are used for comparisons within the experimental arm and for the relative False Positive Fraction.

Non-inferiority and superiority tests

For comparisons of the rTPF, the null and the alternative hypothesis for non-inferiority and superiority tests are

$$H_0: rTPR \leq \exp(-\delta)$$

$$H_a: rTPR > \exp(-\delta)$$

and

$$H_0: rTPR \leq \exp(\theta)$$

$$H_a: rTPR > \exp(\theta)$$

respectively, with non-inferiority and superiority margins equal to $\delta > 0$ and $\theta \geq 0$.

One-sided p-values will be calculated based on the test considered (non-inferiority or superiority).

Switching from non-inferiority to superiority: if the two-sided $(2(1 - \alpha) \times 100)\%$ confidence interval for rTPF not only lies entirely above the non-inferiority margin, but also above the superiority margin, superiority will be claimed at the same alpha-level set for the non-inferiority test. In this case, we will also calculate the p-value associated with a test for superiority.

We will assess the non-inferiority of novel reader combinations involving AI versus SOC for detecting cancers ($\exp(-\delta) = 0.85$). The one-sided α level is set to 0.025. Two-sided 95% confidence intervals will be reported.

For the secondary endpoints, the relative false positive fraction (rFPF, defined as FPF_r/FPF_{SOC} for reader combination r) will be assessed at each stage of radiological assessments: 1. Reader flagging; 2. Consensus discussion; 3. Tissue sampling (biopsy). The rFPF is estimated as $(e+f)/(f+g)$ for each stage of radiological assessments and confidence intervals are computed analogously to the rTPR.

Heterogeneity of treatment effect

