5.3 Setting the operating point of the AI system

A historical calibration dataset from the same institution will be used to set the AI operating point so that AI plus the recorded first reader would have a joint sensitivity 2 % higher than the joint sensitivity of the recorded first and second reader. The AI algorithm outputs a continuous score, and the threshold for the binary flagging decision was set to 0.534 (described in the WHO format research protocol). The threshold has so far not changed over the course of the study.

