5.4 Primary analyses: Non-inferiority

Non-inferiority analyses in terms of sensitivity (rTPF as described on the prior page) of cancer as defined in the primary end-point (4.1) for initial read flagging performed by (i) AI and the first-reader radiologist compared to (ii) the first- and second-reader radiologists. The study has been powered for the primary analysis of cancer at the first screening examination (Figure 3), and adding cases at the subsequent follow-up time-points will further increase the statistical power.

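### Does the 87% power in SAP section 5.7 need correcting because the joint true positive fraction behind it is not stated?

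*Combined protocol and SAP*

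**What the plan says.** SAP section 5.7 bases the sample size on the primary analysis at the screening examination and on a published method for paired screen-positive designs. Its inputs are "A prevalence of breast cancer in the screening of 0.5%, 0.70 TPF for a mammogram", a relative TPF (rTPF) of 1.02 for AI plus radiologist against standard of care (SOC), and full uptake of recommended biopsies. It adds that "The non-inferiority margin was set to 0.85 and a one-sided alpha to 0.025", and concludes: "Based on these assumption, 55,000 women will be included in the study giving a power of 87" per cent.

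The analysis uses the same error rate: under the non-inferiority tests in SAP section 5, "The one-sided α level is set to 0.025", again with a margin of 0.85. That section gives the variance of log rTPF as (b+c)/((a+b)(a+c)), where b and c count cancers flagged by only one of the two combinations.

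SAP section 5.4 defines the primary comparison as "initial read flagging performed by (i) AI and the first-reader radiologist compared to (ii) the first- and second-reader radiologists". Table 1 counts a combination as positive if at least one of its readers flags.

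**The concern.** Section 5.7 presents 87% as the result of its listed assumptions, yet those assumptions leave b+c undetermined. A reader who tries the obvious default, independence of the two combinations, gets 91.3%. Reaching 87% at the stated alpha and margin takes a joint TPF below independence, meaning the two combinations tend to miss different cancers. That is odd for combinations that share a reader, because every cancer the first reader flags is positive on both sides.

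This is the only power justification for the primary non-inferiority claim, and section 5.4 relies on it. Had it been computed for an alpha or margin other than those to be tested, the trial might have less power than it reports.

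**Working it through.** **Inputs.** N = 55,000, prevalence 0.5%, TPF 0.70, rTPF 1.02, margin 0.85 and one-sided alpha 0.025, all from SAP section 5.7. The variance is from SAP section 5. I read 0.70 as the SOC TPF, since the wording "0.70 TPF for a mammogram" does not say which combination it describes.

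**Formula.** Expected cancers: 55,000 × 0.005 = 275. TPF of AI plus first reader: 1.02 × 0.70 = 0.714. With joint TPF J:

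- a+b = 275 × 0.714 = 196.35
- a+c = 275 × 0.70 = 192.5
- b+c = 275 × (1.414 − 2J)
- SE² = (b+c)/((a+b)(a+c)) = (1.414 − 2J)/(275 × 0.714 × 0.70) = (1.414 − 2J)/137.445
- Power = Φ(ln(1.02/0.85)/SE − 1.96), where ln(1.02/0.85) = 0.1823

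**Reproducing 87%.** Solving for 87% gives J = 0.4672: SE = √(0.4796/137.445) = 0.0591 and power = Φ(3.087 − 1.960) = 87.0%. Simulation with the SAP's own confidence interval gives 86.7% at J = 0.467. Power that rounds to 87% needs J between 0.464 and 0.471.

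**Range over the unstated input.** J cannot be below 0.70 + 0.714 − 1 = 0.414 or above 0.70.

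| Joint TPF | SE | Power |
|---|---|---|
| 0.414 (minimum) | 0.0653 | 79.7% |
| 0.467 | 0.0591 | 87.0% |
| 0.4998 (independence, 0.70 × 0.714) | 0.0549 | 91.3% |
| 0.55 | 0.0478 | 96.8% |
| 0.60 | 0.0395 | 99.6% |

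**What J = 0.467 would mean.** AI plus first reader would flag 0.467/0.70 = 66.7% of the cancers SOC flags, but (0.714 − 0.467)/0.30 = 82.3% of those SOC misses, a correlation of −0.16. That is possible but unlikely.

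**Effect of the shared reader.** If the first reader's TPF is s, J is at least s. If AI and the second reader are independent among the cancers the first reader misses, J = s + (0.70 − s)(0.714 − s)/(1 − s):

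- s = 0: J = 0.4998, power 91.3%
- s = 0.40: J = 0.557, power 97.4%
- s = 0.50: J = 0.586, power 99.1%

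These values of s are illustrative. The only first-reader sensitivity in the documents, 77.4% in the retrospective cohort, exceeds the 0.70 assumed for the pair and cannot be used in this model.

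**Other readings.** If 0.70 is the TPF of AI plus first reader, 87% needs J = 0.463 against 0.480 under independence (power 89.5%). If 0.5% is the SOC detection rate, expected cancers are 275/0.70 = 393 and power is 91.6% even at the minimum J. In both cases 87% is lower than independence would give.

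**The case for a change.** The strongest case for a change is that 87% follows from the stated inputs only with an implausible value of an unstated one, while two simple reconstructions reach it by departing from the stated design. The minimum joint TPF with one-sided alpha 0.05 gives 87.4%. Independence with a margin of exp(−0.15) = 0.861 gives 87.1%. If the first was used, power at the stated alpha under that same assumption is 79.7%. The remedy would be cheap: section 5.3 says that "A historical calibration dataset from the same institution will be used to set the AI operating point", and one cross-tabulation of that dataset would give the joint TPF without touching trial data.

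It stands that the joint TPF, or an equivalent discordance rate, is missing and that 0.467 is an unlikely forecast.

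The inference to a different alpha or margin does not stand. Sections 5 and 5.7 both give 0.85 and 0.025, and nothing in the text points elsewhere. Near-matches are also easy to find: independence with one-sided 0.0125 gives 86.0%, and an unpaired test on the difference scale with margin 0.105 gives 86.6%. Independence at the stated alpha and margin gives 87.0% if 47,519 of the 55,000 examinations (86.4%) are evaluable. None of these is documented, so landing near 87% identifies no route. The 79.7% case also requires a first-reader TPF of at most 0.414, since the joint TPF cannot fall below it.

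**Conclusion.** No change follows. Section 5.7 leaves out one planning input, so its power cannot be recomputed exactly. But 87% lies within the 79.7% to nearly 100% that the stated inputs allow, and so it is not shown to be an error. Independence would give 91.3%, about 4 points more, and the shared first reader makes a still higher value likely. A cautious planning value understates power, which is the safe direction.

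Writing the input down would alter no decision. The sample size, alpha, margin and primary analysis stay as they are, and non-inferiority will be judged from the observed confidence interval, whose variance uses the observed b and c. The current SAP version is dated May 16, 2022, with inclusion expected to close in May or June 2022, so the power figure no longer governs recruitment. Analysts who want to report the assumed discordance can do so without amending the plan.

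This rests on reading 0.70 as the SOC TPF, on 275 evaluable cancers and on a true rTPF of 1.02. The two other readings of the inputs checked also leave 87% below the power under independence.
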